Planned study dates	Start of study recruitment / February 2021	End of Recruitment/ December 2023 End of Study/ March 2024
Planned number of study centers	Up to 10 centers which include sites in the US, UK, and EU	
Sample size	Approximately 12 to 24 joints (final number based on an interim analysis and adaptive design)	
Justification of sample size	The proposed sample size is sufficient to provide an acceptable standard error (approximately 0.15) on the Fisher Z scale and yield an acceptable confidence interval width on the population correlation.	
Primary endpoint	
• The correlation between joint-specific tilmanocept uptake value (TUV_{joint}) and the number and area fraction of CD206 expression as determined by IHC assessment.	
Secondary endpoints	
• The correlation between TUV_{joint} and the number and area fraction of CD68 and CD163 determined by IHC assessments.• Classification of synovial anatomic pathology into
• Lympho-myeloid• Diffuse myeloid• Pauci-immune fibroidtypes as a function of CD68, CD163, CD206, CD3, CD20, CD55, and TE7 expression determined by IHC assessments using a multinomial logistic regression model with TUV_{joint} as a covariate.• The correlation between the expression of CD68, CD163, and CD206.	

Exploratory endpoints	
• The correlation of the expression of CD3, CD20, CD55, and TE7 with CD206 as measured through IHC.• The correlation of TUV_{joint} with the expression of CD206, CD163, and CD68 as measured through RNA-seq.• The number and size of CD206, CD163, and CD68 expressing macrophages as measured through (optional) flow cytometry and their correlation with TUV_{joint}.• The correlation between TUV_{global} and synovial anatomic pathology as determined by IHC assessments.• Classification of synovial anatomic pathology into Lympho-myeloid, Diffuse myeloid, and Pauci-immune fibroid types using a multinomial logistic regression model with TUV_{global} as a covariate.
Safety Evaluations	Adverse events, clinical laboratory results (hematology, serum chemistry, vital signs, ECG)

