	
Primary Efficacy Analysis
 
The primary endpoint will be analyzed by computing the Pearson (product-moment) and Spearman (rank) correlation between the TUV_{joint} for the biopsied joint and 2 measures of macrophage prevalence:
 
• The fraction of CD206-expressing macrophages visible in the microscope field under 4x and 10x power magnification, measured as the area fraction (AF) $AF = \frac{\text{Total Stained Area}}{\text{Total Field Area}} \times 100\%.$ 
• The volume of synovial tissue in the biopsied joint derived from the ultrasound synovitis score (Vol). The final CD206-expressing macrophage count is defined as the product of Vol and AF defined above. 
A 95% confidence interval for the population correlation coefficient measuring the association between TUV and CD206 expression (as measured via IHC) will be computed using the Fisher's Z-transformation method ($Z = \tanh^{-1} r$) and its asymptotic Normal approximation. Statistical summaries of the marginal distributions of TUV_{joint} and CD206 macrophage count will be provided (mean, standard deviation, number of cases, median, and range).
 
Secondary Efficacy Analyses
 
The degree of co-expression of CD68, CD163, and/or CD206 macrophage types will be assessed by calculating the Pearson (product-moment) correlations and Spearman rank correlations among these variables. The marginal distributions will be summarized by calculating the mean, standard deviation, number of cases, median, and range for each variable.
 
The ability of TUV_{joint} to discriminate among lympho-myeloid, diffuse myeloid, and pauci-immune fibroid types will be assessed by fitting a multinomial logistic regression model with RA pathotype as the response variable and TUV_{joint} as the explanatory variable. ROC curves will be generated for the multinomial logistic model using the lympho-myeloid type as the base class. No inferential statistics will be generated for this endpoint.

--	---

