### **1.3 Sample Size**

The sample size is expected to be approximately 12 to 24 joints. The final sample size will be determined after the completion of an interim analysis including at least 4 subjects in each pathotype (diffuse myeloid, lympho-myeloid and pauci-immune fibroid). The final sample size will be chosen based on the sponsor's business requirements regarding precision for the estimated correlation between CD206 expressing macrophage density and  $TUV_{joint}$ . The final sample size will be at least  $N = 12$ . If the rarest pathotype has 25% prevalence in the study patient pool, the expected number of subjects at the interim analysis is  $N = 16$ . These needs may be further increased because synovial biopsy fails to recover enough tissue for histological analysis in about 15% of cases.

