#### 4.2.1 Primary Efficacy Variables

The primary endpoint will be analyzed by computing the Pearson (product-moment) and Spearman (rank) correlation coefficient between the TUV for the biopsied joint and the final CD206 expressing macrophage count. The CD206 expressing macrophage count is derived from the IHC histopathology and ultrasound imaging:

- The fraction of CD206 expressing macrophages under 4x and 10x power magnification, defined as the ratio of the total fluorescent stained area to total field area. Specifically, area fraction (AF) is defined as

$$AF = \frac{\text{Total Stained Area}}{\text{Total Field Area}} \times 100\%.$$

- The volume of synovial tissue in the biopsied joint, defined as the ultrasound synovial thickness score (Vol). The CD206 macrophage count will be the product of these 2 variables (that is, CD206 = AF\*Vol).

CD206 expressing macrophage fraction and TUVjoint will be summarized with descriptive statistics (number of data pairs, means, standard deviations, minima, medians, and maxima as well as the Pearson correlation between the variables). The ultrasound synovitis score will be summarized with a frequency table. Defining  $\rho$  to be the population correlation coefficient, a test of the hypotheses

$$\begin{aligned} H_0: \rho &\leq 0 \\ H_a: \rho &> 0 \end{aligned}$$

will be performed using Fisher's Z-transformation and its Normal approximation. A 95% confidence interval for the population correlation coefficient ( $\rho$ ) based on the Fisher Z-transformation (the inverse hyperbolic tangent) and its normal approximation will be provided. The joint distribution of the CD206 macrophage count and TUVjoint will be summarized graphically with a scatter diagram of the data pairs with the least-squares regression line superimposed on the graph. The joint distribution of the component variables of CD206 macrophage count will be graphically summarized with box plots showing the conditional distribution of TUVjoint for each category of synovitis score.

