## Appendix B – Table Shells

Page x of y

Table 1. Subject Disposition  
Navidea Biopharmaceuticals - Study No. NAV3-32

	Overall
Screen Failures	xx
Enrolled	xx
Completed	xx (xxx%)
Withdrawn	xx (xxx%)
Reason for Withdrawal	
Adverse Event	xx (xxx%)
Protocol Violation	xx (xxx%)
Lost to Follow-Up	xx (xxx%)
Withdrawal of Consent	xx (xxx%)
Sponsor Discretion	xx (xxx%)
Investigator Discretion	xx (xxx%)
Death	xx (xxx%)
Other	xx (xxx%)

Table 2. Demographics and Baseline Data Descriptive Statistics - Continuous Variables  
Navidea Biopharmaceuticals - Study No. NAV3-32  
Safety Population (N=xxx)

	Mean	Std Dev	n	Min	Max	Median
Age (years)	xxx	xxx	xxx	xxx	xxx	xxx
Height (inches)	xxx	xxx	xxx	xxx	xxx	xxx
Weight (pounds)	xxx	xxx	xxx	xxx	xxx	xxx

---

STATKING Clinical Services (DD-MMM-YYYY)  
Source Program: xxxxxxxx.sas

Table 3. Demographics and Baseline Data Descriptive Statistics - Categorical Variables  
Navidea Biopharmaceuticals - Study No. NAV3-32  
Safety Population (N=xxx)

Variable	Category	Overall
Gender	Male	xx (xxx%)
	Female	xx (xxx%)
Race	American Indian or Alaska Native	xx (xxx%)
	Asian	xx (xxx%)
	Black or African American	xx (xxx%)
	Native Hawaiian or Other Pacific Islander	xx (xxx%)
	White	xx (xxx%)
	Other	xx (xxx%)
Ethnicity	Hispanic or Latino	xx (xxx%)
	Not Hispanic or Latino	xx (xxx%)

---

STATKING Clinical Services (DD-MMM-YYYY)  
Source Program: xxxxxxxx.sas

Page x of y

Table 4. Descriptive Statistics of TUVjoint and the CD206 Expressing Macrophage Fraction  
 Navidea Biopharmaceuticals - Study No. NAV3-32  
 ITA Population (N=xxx)

Measure /Biomarker	Mean	Std Dev	n	Min	Max	Median	Pearson (Product-Moment) Correlation	95% Confidence Limits a	Spearman (Rank) Correlation	95% Confidence Limits b
							Coefficient		Coefficient	
CD206	xxx	xxx	xxx	xxx	xxx	xxx	x.xxxx	(x.xxxx, x.xxxx)	x.xxxx	(x.xxxx, x.xxxx)
TUV joint	xxx	xxx	xxx	xxx	xxx	xxx				

a 95% Confidence limits for the Pearson (Product-Moment) Correlation Coefficient are based on the Fisher Z-Transformation (the inverse hyperbolic tangent) and its normal approximation.

b 95% Confidence limits for the Spearman (Rank) Correlation Coefficient are based on the Fisher Z-Transformation (the inverse hyperbolic tangent) and its normal approximation.

STATKING Clinical Services (DD-MMM-YYYY)

Source Program: xxxxxxxx.sas

Table Format is Repeated for the PP Population (Table 5)

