Table 22. Pearson (Product-Moment) Correlation of CD3, CD20, CD55, CD68, CD163, CD206, and TE7 Biomarkers Association with TUVjoint Measured by IHC Measurement  
 Navidea Biopharmaceuticals - Study No. NAV3-32  
 ITA Population (N=xxx)

Measure /Biomarker	Pearson (Product-Moment) Correlation a	95% Confidence Limits b	n c
TUV joint	--	--	xxx
CD3	x.xxx	(x.xxx, x.xxx)	xxx
CD20	x.xxx	(x.xxx, x.xxx)	xxx
xxx	x.xxx	(x.xxx, x.xxx)	xxx
CD206	x.xxx	(x.xxx, x.xxx)	xxx
TE7	x.xxx	(x.xxx, x.xxx)	xxx

a Pearson (Product-Moment) correlation between TUVjoint and the indicated measurement/biomarker.

b Confidence limits calculated using the Fisher Z-transformation.

c Number of complete data points.

STATKING Clinical Services (DD-MMM-YYYY)

Source Program: xxxxxxx.sas

Table Format is Repeated for RNAseq and Flow Cytometry (Tables 24, 26). Each table will be repeated for the PP Population (Tables 23, 25, 27).

Page x of y

Table 28. Spearman (Rank) Correlation of CD3, CD20, CD55, CD68, CD163, CD206, and TE7 Association with TUVjoint Measured by IHC Measurement  
 Navidea Biopharmaceuticals - Study No. NAV3-32  
 ITA Population (N=xxx)

Measure /Biomarker	Spearman (Rank) Correlation a	95% Confidence Limits b	n c
TUV joint	--	--	xxx
CD3	x.xxx	(x.xxx, x.xxx)	xxx
CD20	x.xxx	(x.xxx, x.xxx)	xxx
xxx	x.xxx	(x.xxx, x.xxx)	xxx
CD206	x.xxx	(x.xxx, x.xxx)	xxx
TE7	x.xxx	(x.xxx, x.xxx)	xxx

a Spearman (Rank) correlation between TUVjoint and the indicated measurement/biomarker.

b Confidence limits calculated using the Fisher Z-transformation.

c Number of complete data points.

STATKING Clinical Services (DD-MMM-YYYY)

Source Program: xxxxxxx.sas

Table Format is Repeated for RNAseq and Flow Cytometry (Tables 30, 32). Each table will be repeated for the PP Population (Tables 29, 31, 33).

Table 34. Descriptive Statistics of CD3, CD20, CD55, CD68, CD163, CD206, and TE7 Biomarkers Association  
with TUVjoint Measured by IHC Measurement  
Navidea Biopharmaceuticals - Study No. NAV3-32  
ITA Population (N=xxx)

Measure /Biomarker	n a	Mean	Std Dev	Min	Max	Median
TUV joint	xxx	xxx	xxx	xxx	xxx	xxx
CD3	xxx	xxx	xxx	xxx	xxx	xxx
CD20	xxx	xxx	xxx	xxx	xxx	xxx
xxx	xxx	xxx	xxx	xxx	xxx	xxx
CD206	xxx	xxx	xxx	xxx	xxx	xxx
TE7	xxx	xxx	xxx	xxx	xxx	xxx

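### The SAP's Spearman limits use the Pearson Fisher-Z approximation and cover less than 95% at moderate-to-high correlation

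*SAP*

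**What the plan says.** SAP Section 4.2.1 computes Pearson and Spearman coefficients between TUV_joint and the CD206 count. It then plans a one-sided test of ρ ≤ 0 against ρ > 0 using Fisher's "Z-transformation and its Normal approximation", with a 95% interval by the same route. It does not say which of the two coefficients carries the test and the interval, and it states no significance level. The protocol synopsis likewise relies on Fisher Z "and its asymptotic Normal approximation".

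The limits for each coefficient are described only in the table shells of SAP Appendix B:

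- Table 4 (repeated as Table 5), footnote a: "95% Confidence limits for the Pearson (Product-Moment) Correlation Coefficient are based on the Fisher Z-Transformation". Footnote b: "95% Confidence limits for the Spearman (Rank) Correlation Coefficient are based on the Fisher Z-Transformation". Both continue with the same reference to the normal approximation.
- Table 28 (repeated through Table 33), and Table 44, whose layout is reused for Spearman in Tables 46–47: "Confidence limits calculated using the Fisher Z-transformation".
- Table 8, whose layout is reused for Spearman in Tables 10–11: a column of 95% limits, but the only footnote defines n and no interval method is named.

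Neither document writes out a variance, mentions a correction for ranks, or plans a bootstrap interval, a transformation or a check of normality. On size, SAP Section 1.3 says: "The sample size is expected to be approximately 12 to 24 joints".

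**The concern.** The variance 1/(n−3) for atanh(r) is a result for the Pearson coefficient under bivariate normality. The Spearman coefficient has a larger variance on that scale, and the excess grows with the correlation. Using one formula for both makes the Spearman limits too tight where the correlation is high, which is the result the study hopes for.

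The sample size is justified by precision and interval width rather than power, so the limits are a main product of the analysis and should have the coverage they claim. The tables affected are the primary one (Tables 4–5) and the secondary and exploratory Spearman tables.

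**Working it through.** **Inputs.** n = 12, 16 and 24, from the planned 12 to 24 joints and the SAP's expected interim size of 16. The 95% level is from the SAP and the protocol. The variance 1/(n−3) is an assumption: it is the ordinary meaning of Fisher Z with its normal approximation, but neither document prints it.

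**The plan's own precision figure.** The protocol synopsis cites an "acceptable standard error (approximately 0.15) on the Fisher Z scale". With SE = 1/√(n−3):

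- n = 12: 1/√9 = 0.333
- n = 16: 1/√13 = 0.277
- n = 24: 1/√21 = 0.218

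An SE of 0.15 needs n = 3 + 1/0.15² = 47.4, so the figure does not reproduce anywhere in 12 to 24. That is a separate issue. It matters here only because it cannot be used to infer what variance the sponsor intends.

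**Coverage of the planned Spearman limits.** Limits are tanh(atanh r ± 1.96/√(n−3)). Bivariate normal data were simulated with 40,000 samples per setting, and the target was the true Spearman value (6/π)·asin(ρ/2). Ranges are over n = 12 to 24.

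| Underlying ρ | Coverage, variance 1/(n−3) |
|---|---|
| 0 | 94.7–95.0% |
| 0.5 | 94.2–94.5% |
| 0.7 | 93.6–94.1% |
| 0.8 | 93.2–93.7% |
| 0.9 | 91.8–92.0% |

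At n = 12 the actual SD of Z is 0.335 at ρ = 0, 0.351 at 0.7 and 0.382 at 0.9, against a nominal 0.333. Rank coefficients do not change under monotone transformation, so the same coverage applies to lognormal data built from these normals. A one-sided 5% Spearman test at ρ = 0 rejects 4.9–5.1%, so the null error rate is not inflated.

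**With variance (1 + r²/2)/(n−3)** (Bonett–Wright). The SE is multiplied by √(1 + r²/2): 1.06 at r = 0.5, 1.12 at 0.7 and 1.19 at 0.9. Simulated coverage on the same normal data is 95.0–96.3%, with the highest values near zero correlation.

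**Effect on printed limits.**

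- n = 12, r = 0.9: atanh r = 1.472. Planned lower limit tanh(1.472 − 1.96 × 0.333) = 0.67. Corrected SE = √(1.405/9) = 0.395, giving tanh(1.472 − 0.774) = 0.60.
- n = 16, r = 0.5: atanh r = 0.549. Planned tanh(0.5493 − 0.5436) = 0.006. Corrected SE = √(1.125/13) = 0.294, giving tanh(0.549 − 0.577) = −0.027.
- n = 12, r = 0.7: the lower limit moves from 0.211 to 0.137.
- n = 24, r = 0.7: the lower limit moves from 0.413 to 0.371.

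**Pearson, under assumed distributions.** On normal data, coverage is 94.9–95.1%. For skew, assume lognormal AF (CV 0.5 to 1.2), Vol of 2 or 3, and lognormal TUV (CV 0.3 to 0.6). Raw-scale coverage is then 82–94% at underlying ρ 0.5–0.9. Under independence, a nominal one-sided 2.5% test rejects about 3.1–4.4%. The 2.5% level is itself assumed.

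**The case against.** The loss is modest: 0.5 to 1.5 points at ρ 0.5–0.7, and about 3 points only at 0.9. At n = 12, r = 0.9 both lower limits are far above zero, so no conclusion about a positive correlation changes. Most of the affected tables are secondary or exploratory. All of this stands and keeps the point small. It does not remove it, since the n = 16, r = 0.5 example shows a limit crossing zero.

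The shortfall also depends on the data. Choosing the highest and lowest TUV_joint alternately may cluster that variable. In an assumed case with two-cluster TUV and lognormal AF times a Vol of 2 or 3, the planned Spearman limits cover 94.4–95.6% and the corrected ones 95.8–97.6%. There the correction errs towards wide intervals.

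A reader might go further and infer that all the printed intervals are too narrow, or that the primary test rejects too often because the data are skewed. The documents do not support either reading:

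- Neither gives a distribution or prior data for TUV_joint or AF. The primary variable is defined only by formula ("The CD206 macrophage count will be the product of these 2 variables").
- Protocol Section 1.1 describes high macrophage densities in two pathotypes and few in a less common third. That may mean a minority of values near zero rather than a long right tail.
- In the two-cluster case the Pearson limits cover 95.4–97.3%. With one-third of joints assumed fibroid at a tenth of the AF of the rest, a one-sided 2.5% test rejects 2.7–2.9%.
- With only one variable skewed (lognormal sigma 0.5), Pearson coverage is 94.7–97.0%.
- A type I error of 5.0% at nominal 2.5% appears only with TUV CV at 1.0.

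**Conclusion.** The Spearman point holds. On the ordinary reading of the footnotes, the limits in Tables 4–5, 28–33 and 46–47 fall short of 95% at moderate-to-high correlation: about 94% at ρ 0.5–0.7, 93–94% at 0.8 and 92% at 0.9. Near zero they are essentially right. This rests on two assumptions: that 1/(n−3) is what will be programmed, and that the data are bivariate normal or a monotone transformation of it.

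The Pearson point survives only as a condition. If both TUV_joint and AF × Vol are right-skewed, the raw-scale limits and the one-sided test can be anti-conservative, at about 3.1–4.4% for a nominal 2.5% in the assumed range. That justifies a safeguard, not a finding that the primary analysis is wrong.

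**What to change.** 1. In the footnotes that govern the Spearman limits in Tables 4–5, 28–33 and 46–47, state the variance as (1 + r²/2)/(n−3). Add the same footnote to Tables 10–11. Leave the Pearson footnotes as they are.
2. In SAP Section 4.2.1, name the coefficient that carries the primary interval and test, and state the one-sided level.
3. Report a permutation p-value for r with the primary test. It guards the error rate under independence whatever the two distributions are.

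A log-scale Pearson interval is not recommended unless the SAP first gives a rule for AF = 0, where the logarithm is undefined.

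The cost is a few lines of SAS and slightly wider Spearman intervals, mildly conservative near zero correlation. SAP Appendix A says that footnote changes after approval are charged, so the edit is best made before then.

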	Day 0 - 60 to 75 Minutes Post Admin	RAW	xxx	xxx	xxx	xxx	xxx	xxx
		CFB	xxx	xxx	xxx	xxx	xxx	xxx
xxxxxxxxxxxxxxxxxx	Screening	RAW	xxx	xxx	xxx	xxx	xxx	xxx
	Day 0 - 60 to 75 Minutes Post Admin	RAW	xxx	xxx	xxx	xxx	xxx	xxx
		CFB	xxx	xxx	xxx	xxx	xxx	xxx

a RAW = data recorded in database; CFB = change from baseline = (parameter value at the current time point)-(Baseline parameter value).  
STATKING Clinical Services (DD-MMM-YYYY)  
Source Program: xxxxxxx.sas

Table 54. ECG Parameters Descriptive Statistics  
 Navidea Biopharmaceuticals - Study No. NAV3-32  
 Safety Population (N=xxx)

ECG Parameter (units)	Visit	Data Type a	n	Std Dev	Mean	Min	Max	Median
xxxxxxxxxxxxxxxxxxxx (xxx)	Baseline	RAW	xxx	xxx	xxx	xxx	xxx	xxx
	30 Minute Post Admin	RAW	xxx	xxx	xxx	xxx	xxx	xxx
		CFB	xxx	xxx	xxx	xxx	xxx	xxx
xxxxxxxxxxxxxxxxxxxx (xxx)	Baseline	RAW	xxx	xxx	xxx	xxx	xxx	xxx
	30 Minute Post Admin	RAW	xxx	xxx	xxx	xxx	xxx	xxx
		CFB	xxx	xxx	xxx	xxx	xxx	xxx
xxxxxxxxxxxxxxxxxxxx (xxx)	Baseline	RAW	xxx	xxx	xxx	xxx	xxx	xxx
	30 Minute Post Admin	RAW	xxx	xxx	xxx	xxx	xxx	xxx
		CFB	xxx	xxx	xxx	xxx	xxx	xxx
xxxxxxxxxxxxxxxxxxxx (xxx)	Baseline	RAW	xxx	xxx	xxx	xxx	xxx	xxx
	30 Minute Post Admin	RAW	xxx	xxx	xxx	xxx	xxx	xxx
		CFB	xxx	xxx	xxx	xxx	xxx	xxx

a RAW = data recorded in database; CFB = change from baseline = (parameter value at the current time point)-(Baseline parameter value).  
 STATKING Clinical Services (DD-MMM-YYYY)  
 Source Program: xxxxxxxx.sas

Table 55. Summary of Treatment Emergent Adverse Events  
Navidea Biopharmaceuticals - Study No. NAV3-32  
Safety Population (N=xxxx)

Overall	
Subjects with at Least One Treatment Emergent Adverse Event (TEAE)	xxx (xxx%)
Maximum TEAE Severity Grade	
Mild	xxx (xxx%)
Moderate	xxx (xxx%)
Severe	xxx (xxx%)
Highest Relationship of TEAE to Study Drug	
Definitely Not [n(%)]	xxx (xxx%)
Probably Not [n(%)]	xxx (xxx%)
Possibly [n(%)]	xxx (xxx%)
Probably [n(%)]	xxx (xxx%)
Definitely [n(%)]	xxx (xxx%)
Highest Relationship of TEAE to Study Procedure	
Definitely Not [n(%)]	xxx (xxx%)
Probably Not [n(%)]	xxx (xxx%)
Possibly [n(%)]	xxx (xxx%)
Probably [n(%)]	xxx (xxx%)
Definitely [n(%)]	xxx (xxx%)

Table 56. Number and Percent of Subjects with TEAEs  
Navidea Biopharmaceuticals - Study No. NAV3-32  
Safety Population (N=xxxx)

Adverse Event Category a :	Overall
Total Number of Treatment Emergent Adverse Events (TEAEs)	xxx
Subjects with at Least One TEAE	xxx (xxx%)
System Organ Class 1	xxx (xxx%)
Preferred Term 1	xxx (xxx%)
Preferred Term 2	xxx (xxx%)
System Organ Class 2	xxx (xxx%)
Preferred Term 1	xxx (xxx%)
Preferred Term 2	xxx (xxx%)

a Adverse events coded with MedDRA Coding Dictionary Version XXX.  
STATKING Clinical Services (DD-MMM-YYYY)  
Source Program: xxxxxxx.sas

Table 57. Descriptive Statistics of TUVjoint by Fibroid vs. Non-Fibroid Type  
Navidea Biopharmaceuticals - Study No. NAV3-32  
ITA Population (N=xxx)

Type	n a	Mean	Std Dev	Min	Max	Median
Fibroid	xxx	xxx	xxx	xxx	xxx	xxx
non-Fibroid	xxx	xxx	xxx	xxx	xxx	xxx

---

a Number of complete data points  
STATKING Clinical Services (DD-MMM-YYYY)  
Source Program: xxxxxxx.sas

Table Format is Repeated for TUVglobal (Table 59). Tables will be repeated for the PP Population (Tables 58, 60).

Figure 1. Scatterplot of the Joint Distribution of CD206 Macrophage Count and TUVjoint  
Navidea Biopharmaceuticals - Study No. NAV3-32  
ITA Population (N=xxx)

[figure not shown]
[figure not shown]

Figure 2. Boxplots of the Conditional Distribution of  $TUV_{joint}$  by Synovitis Score  
Navidea Biopharmaceuticals - Study No. NAV3-32  
ITA Population (N=xxx)

[figure not shown]

---

STATKING Clinical Services (DD-MMM-YYYY)  
Source Program: xxxxxxx.sas

Table Format is Repeated for  $TUV_{global}$  (Figure 3).

Figure 4. ROC Curves by RA Disease Type, Logistic Regression with TUVjoint  
Navidea Biopharmaceuticals - Study No. NAV3-32  
ITA Population (N=xxx)

STATKING Clinical Services (DD-MMM-YYYY)  
Source Program: xxxxxxx.sas

Table Format is Repeated for TUVglobal (Figure 5).

Figure 6. Conditional Distribution of TUVjoint by RA Disease Type  
Navidea Biopharmaceuticals - Study No. NAV3-32  
ITA Population (N=xxx)

[figure not shown]
[figure not shown]
[figure not shown]

Figure 7. Joint Distribution of CD3, CD20, CD55, CD68, CD163, CD206, and TE7 Biomarkers  
Association with  $TUV_{Joint}$   
Navidea Biopharmaceuticals - Study No. NAV3-32  
ITA Population (N=xxx)

[figure not shown]
STATKING Clinical Services (DD-MMM-YYYY)  
Source Program: xxxxxxx.sas

Figure 8. Joint Distribution of CD68, CD163, and CD206 in mRNA  
Navidea Biopharmaceuticals - Study No. NAV3-32  
ITA Population (N=xxx)

STATKING Clinical Services (DD-MMM-YYYY)  
Source Program: xxxxxxx.sas

Figure 9. Joint Distribution of CD68, CD163, and CD206 Measured by Flow Cytometry  
Navidea Biopharmaceuticals - Study No. NAV3-32  
ITA Population (N=xxx)

Page x of y

Data Listing 1. Subject Disposition Data Listing  
Navidea Biopharmaceuticals - Study No. NAV3-32

Subject No.	Disposition Status	Date of Completion/ Withdrawal/Screen Fail	Withdrawal Reason
xxxx	xxxxxxxxxxxxxxxxxxxx	xxxxxxxx	xxxxxxxxxxxxxxxxxxxx
xxxx	xxxxxxxxxxxxxxxxxxxx	xxxxxxxx	xxxxxxxxxxxxxxxxxxxx
xxxx	xxxxxxxxxxxxxxxxxxxx	xxxxxxxx	xxxxxxxxxxxxxxxxxxxx
xxxx	xxxxxxxxxxxxxxxxxxxx	xxxxxxxx	xxxxxxxxxxxxxxxxxxxx

---

STATKING Clinical Services (DD-MMM-YYYY)  
Source Program: xxxxxxxx.sas

Page x of y

Data Listing 2. Inclusion/Exclusion Data Listing  
Navidea Biopharmaceuticals - Study No. NAV3-32

Subject No.	Did Subject Meet All Eligibility Criteria?	Criterion Category	Criterion	Was a Waiver Granted?	Is Subject a Screen Failure?
xxxx	xxxx	xxxxxxxxxxxxxxxxxxxxxxxxxxxx	xxxxxxxxxx	xxxx	xxxx
xxxx	xxxx	xxxxxxxxxxxxxxxxxxxxxxxxxxxx	xxxxxxxxxx	xxxx	xxxx
xxxx	xxxx	xxxxxxxxxxxxxxxxxxxxxxxxxxxx	xxxxxxxxxx	xxxx	xxxx
xxxx	xxxx	xxxxxxxxxxxxxxxxxxxxxxxxxxxx	xxxxxxxxxx	xxxx	xxxx

---

STATKING Clinical Services (DD-MMM-YYYY)  
Source Program: xxxxxxx.sas

Page x of y

Data Listing 3. Protocol Deviations Data Listing  
Navidea Biopharmaceuticals - Study No. NAV3-32

Subject No.	Date of Deviation	Deviation Description	Deviation Category (Major/Minor)
xxxx	xxxxxx	xxxxxxxxxxxxxxxxxxxxxxxxxxxx	xxxxxxxxxx
xxxx	xxxxxx	xxxxxxxxxxxxxxxxxxxxxxxxxxxx	xxxxxxxxxx
xxxx	xxxxxx	xxxxxxxxxxxxxxxxxxxxxxxxxxxx	xxxxxxxxxx
xxxx	xxxxxx	xxxxxxxxxxxxxxxxxxxxxxxxxxxx	xxxxxxxxxx

---

STATKING Clinical Services (DD-MMM-YYYY)  
Source Program: xxxxxxxx.sas

Page x of y

Data Listing 4. Demographics Data Listing  
Navidea Biopharmaceuticals - Study No. NAV3-32  
Safety Population (N=xxx)

Subject No.	Informed Consent Date/Time	Date of Birth	Height (inches)	Weight (pounds)	Age (yrs)	Gender	Race	Ethnicity
xxxx	xxxxxx	xxxxxx	xxx	xxx	xxx	xxxxxx	xxxxxx	xxxxxx
xxxx	xxxxxx	xxxxxx	xxx	xxx	xxx	xxxxxx	xxxxxx	xxxxxx
xxxx	xxxxxx	xxxxxx	xxx	xxx	xxx	xxxxxx	xxxxxx	xxxxxx
xxxx	xxxxxx	xxxxxx	xxx	xxx	xxx	xxxxxx	xxxxxx	xxxxxx

---

STATKING Clinical Services (DD-MMM-YYYY)  
Source Program: xxxxxxxx.sas

Page x of y

Data Listing 5. Subjects Excluded from ITA Population Data Listing  
Navidea Biopharmaceuticals - Study No. NAV3-32  
All Enrolled Subjects (N=xxx)

Subject No.	Reason for Exclusion
xxxx	xxxxxxxxxxxxxxxxxxxxxxxxxxxx

---

STATKING Clinical Services (DD-MMM-YYYY)  
Source Program: xxxxxxx.sas

Page x of y

Data Listing 6. Subjects Excluded from PP Population Data Listing  
Navidea Biopharmaceuticals - Study No. NAV3-32  
All Enrolled Subjects (N=xxx)

Subject No.	Reason for Exclusion
xxxx	xxxxxxxxxxxxxxxxxxxxxxxxxxxx

---

STATKING Clinical Services (DD-MMM-YYYY)  
Source Program: xxxxxxxx.sas

Page x of y

Data Listing 7. Subjects Excluded from Safety Population Data Listing  
Navidea Biopharmaceuticals - Study No. NAV3-32  
All Enrolled Subjects (N=xxx)

Subject No.	Reason for Exclusion
xxxx	xxxxxxxxxxxxxxxxxxxxxxxxxxxx

---

STATKING Clinical Services (DD-MMM-YYYY)  
Source Program: xxxxxxx.sas

Page x of y

Data Listing 8. Medical History Data Listing  
Navidea Biopharmaceuticals - Study No. NAV3-32  
Safety Population (N=xxx)

Subject No.	MedDRA System Organ Class a /		Start Date	Resolution/Stop	
	MedDRA Preferred Term/ CRF Verbatim Term	CRF Verbatim Term		Date	Ongoing?
xxxx	xxxxxxxxxxxxxxxxxxxxxxxxxxxxxx	xxxxxxxx	xxxxxxxx	xxxxxxxx	xxx
	xxxxxxxxxxxxxxxxxxxxxxxxxxxxxx	xxxxxxxx	xxxxxxxx	xxxxxxxx	xxx
	xxxxxxxxxxxxxxxxxxxxxxxxxxxxxx	xxxxxxxx	xxxxxxxx	xxxxxxxx	xxx

a Medical history terms coded with MedDRA Coding Dictionary Version xxx.  
STATKING Clinical Services (DD-MMM-YYYY)  
Source Program: xxxxxxxx.sas

Page x of y

Data Listing 9. Prior and Concomitant Medications Data Listing  
Navidea Biopharmaceuticals - Study No. NAV3-32  
Safety Population (N=xxxx)

Subject No.	Drug Preferred Term a / Verbatim/ ATC Level 1 Text/ ATC Level 4 Text	Indication	Frequency	Start	Stop	Route	Ongoing?
				Date	Date		
xxxxxx	xxxxxxxxxxxxxxxxxxxxxxxxxxxxxx	xxxxxx	xxxxxx	xxxxxx	xxxxxx	xxxx	xxxx
	xxxxxxxxxxxxxxxxxxxxxxxxxxxxxx						
	xxxxxxxxxxxxxxxxxxxxxxxxxxxxxx						
	xxxxxxxxxxxxxxxxxxxxxxxxxxxxxx						
	xxxxxxxxxxxxxxxxxxxxxxxxxxxxxx						
xxxxxx	xxxxxxxxxxxxxxxxxxxxxxxxxxxxxx	xxxxxx	xxxxxx	xxxxxx	xxxxxx	xxxx	xxxx
	xxxxxxxxxxxxxxxxxxxxxxxxxxxxxx						
	xxxxxxxxxxxxxxxxxxxxxxxxxxxxxx						
	xxxxxxxxxxxxxxxxxxxxxxxxxxxxxx						
	xxxxxxxxxxxxxxxxxxxxxxxxxxxxxx						

a Medications coded with WHO Coding Dictionary xxxxxxxxx  
STATKING Clinical Services (DD-MMM-YYYY)  
Source Program: xxxxxxx.sas

Page x of y

Data Listing 10. Prior and Concomitant RA Medications Data Listing  
Navidea Biopharmaceuticals - Study No. NAV3-32  
Safety Population (N=xxxx)

Subject No.	Drug Preferred Term a / Verbatim/ Indication/ ATC Level 1 Text/ ATC Level 4 Text	Frequency	Start Date	Stop Date	Route	Ongoing?
xxxxxxxxxx	xxxxxxxxxxxxxxxxxxxxxxxxxxxxxx xxxxxxxxxxxxxxxxxxxxxxxxxxxxxx xxxxxxxxxxxxxxxxxxxxxxxxxxxxxx xxxxxxxxxxxxxxxxxxxxxxxxxxxxxx xxxxxxxxxxxxxxxxxxxxxxxxxxxxxx	xxxxxxx	xxxxxxx	xxxxxxx	xxxxxx	xxxxx
xxxxxxxxxx	xxxxxxxxxxxxxxxxxxxxxxxxxxxxxx xxxxxxxxxxxxxxxxxxxxxxxxxxxxxx xxxxxxxxxxxxxxxxxxxxxxxxxxxxxx xxxxxxxxxxxxxxxxxxxxxxxxxxxxxx xxxxxxxxxxxxxxxxxxxxxxxxxxxxxx	xxxxxxx	xxxxxxx	xxxxxxx	xxxxxx	xxxxx

a Medications coded with WHO Coding Dictionary xxxxxxxxx  
STATKING Clinical Services (DD-MMM-YYYY)  
Source Program: xxxxxxxx.sas

Data Listing 11. Adverse Events Data Listing  
Navidea Biopharmaceuticals - Study No. NAV3-32  
Safety Population (N=xxxx)

Subject No.	Start Date and Time	End Date and Time	Start Date and Time of	MedDRA System	Relation to Tc-99m	tilmanocept/ Procedure	Serious?	Outcome
			Nearest Previous Time/ Injection	Organ Class a / MedDRA Preferred Term/ CRF Verbatim Term				
xxxxxxxxxx	xxxxxxx	xxxxxxx	xxxxxxxxxxxxxxxxxxxx	xxxxxxxxxxxx	xxxxxxxx/	xxx	xxxxxxxx	
	xxxxxx/	xxxxxx	xxxxxxxxxxxxxxxxxxxx	xxxxxxxxxxxx	xxxxxxxx			
	xxxxxx		xxxxxxxxxxxxxxxxxxxx					
	xxxxxx							
xxxxxxxxxx	xxxxxxx	xxxxxxx	xxxxxxxxxxxxxxxxxxxx	xxxxxxxx	xxxxxxxx/	xxx	xxxxxxxx	
	xxxxxx/	xxxxxx	xxxxxxxxxxxxxxxxxxxx	xxxxxxxxxxxx	xxxxxxxx			
	xxxxxx		xxxxxxxxxxxxxxxxxxxx					
	xxxxxx							

a Adverse events coded with MedDRA Coding Dictionary Version xxx.  
STATKING Clinical Services (DD-MMM-YYYY)  
Source Program: xxxxxxxx.sas

Page x of y

Data Listing 12. Occurrence of TEAEs Associated with Concomitant Medication or Class of Medications

